#### 7.2.4 Visit 5: Day $8 \pm 2$ Days

The following activities will be conducted:

- Collect vital signs (blood pressure, heart rate, respiratory rate, and temperature) after subject has been seated for ≥2 minutes (see Section 8.1.2).
- Subject to complete the GSP assessment; will be conducted from 7:00 am to 11:00 am.
- Subject to complete HDSM-Ax assessment.
  - o Subject to complete PGI-S administered as Question #6 at the end of the HDSM-Ax questionnaire.
- Perform local tolerability assessments.
- Review changes to the subject's health (AEs).
- Evaluate subject compliance:
  - Ask subjects whether they applied the study product to the right and left axilla each evening as directed and confirm reason for any missed doses.
  - o Verbally confirm application process.
- Review concomitant medications/treatments.
- Schedule the subject to return for the next study visit.

## 7.2.5 Visit 6: Day $15 \pm 2$ Days

The following activities will be conducted:

- Collect vital signs (blood pressure, heart rate, respiratory rate, and temperature) after subject has been seated for ≥2 minutes.
- Subject to complete the GSP assessment; will be conducted from 7:00 am to 11:00 am.
- Subject to complete HDSM-Ax assessment.
  - o Subject to complete PGI-S administered as Question #6 at the end of the HDSM-Ax questionnaire.
- Subject to complete the DLQI questionnaire.
- Perform local tolerability assessments.
- Review changes to the subject's health (AEs).
- Evaluate subject compliance:
  - Ask subjects whether they applied the study product to the right and left axilla each evening as directed and confirm reason for any missed doses.
  - Verbally confirm application process.
- Review concomitant medications/treatments.
- Remind subject to bring their study medication to next visit.
- Schedule the subject to return for the next study visit.

## 7.2.6 Visit 7: Day $22 \pm 2$ Days

The following activities will be conducted:

- Collect vital signs (blood pressure, heart rate, respiratory rate, and temperature) after subject has been seated for ≥2 minutes.
- Subject to complete the GSP assessment; will be conducted from 7:00 am to 11:00 am.
- Subject to complete HDSM-Ax assessment.
  - o Subject to complete PGI-S administered as Question #6 at the end of the HDSM-Ax questionnaire.
- Perform local tolerability assessments.
- Review changes to the subject's health (AEs).
- Evaluate subject compliance:
  - Ask subjects whether they applied the study product to the right and left axilla each evening as directed and confirm reason for any missed doses.
  - Verbally confirm application process.
- Collect subject's previously dispensed study product container, weigh with the applicator cap on, and record weight of container.
- Dispense study product container (2 of 2).
  - O Access the IRT system to obtain the number of the next assigned pump container to dispense. Pull from inventory the pump container whose unique identifier matches that assigned by the IRT system. Record the unique IP gel pump container number on the source document.
  - o Write subject number and initials on the study product container label.
  - o Prime the pump (5 actuations) and discard expressed gel.
  - Weigh the primed pump with the applicator cap on and record in source prior to dispensing to the subject.
- Review concomitant medications/treatments.
- Schedule the subject to return for the next study visit.

## 7.2.7 Visit 8: Day $29 \pm 2$ Days

The following activities will be conducted:

- Collect vital signs (blood pressure, heart rate, respiratory rate, and temperature) after subject has been seated for ≥2 minutes.
- Subject to complete the GSP assessment; will be conducted from 7:00 am to 11:00 am.
- Subject to complete HDSM-Ax assessment.
  - o Subject to complete PGI-S administered as Question #6 at the end of the HDSM-Ax questionnaire.
- Perform local tolerability assessments.
- Review changes to the subject's health (AEs).
- Evaluate subject compliance:
  - Ask subjects whether they applied the study product to the right and left axilla each evening as directed and confirm reason for any missed doses.

o Verbally confirm application process.

- Perform UPT if applicable (FOCBP only). If positive, the subject shall be withdrawn from the study.
- Review concomitant medications/treatments.
- Schedule the subject to return for the next study visit.

#### 7.2.8 Visit 9: Day $36 \pm 2$ Days

The following activities will be conducted:

- Collect vital signs (blood pressure, heart rate, respiratory rate and temperature) after subject has been seated for ≥2 minutes.
- Subject to complete the GSP assessment; will be conducted from 7:00 am to 11:00 am.
- Subject to complete HDSM-Ax assessment.
  - o Subject to complete PGI-S administered as Question #6 at the end of the HDSM-Ax questionnaire.
- Perform local tolerability assessments.
- Review changes to the subject's health (AEs).
- Evaluate subject compliance:
  - Ask subjects whether they applied the study product to the right and left axilla each evening as directed and confirm reason for any missed doses.
  - Verbally confirm application process.
- Review concomitant medications/treatments.
- Schedule the subject to return for the next study visit.

#### 7.2.9 Visits 10 and 11: GSP4 (Day 41) $\pm$ 2 Days and GSP 5 (Day 42) $\pm$ 2 Days

**Visits 10** and **11** will occur as separate visits on Days 41 and 42.

The following activities will be conducted:

- Subject to complete the GSP assessment; will be conducted from 7:00 am to 11:00 am.
- Subject to complete HDSM-Ax assessment.
  - o Subject to complete PGI-S administered as Question #6 at the end of the HDSM-Ax questionnaire.
- Review changes to the subject's health (AEs).
- Evaluate subject compliance:
  - Ask subjects whether they applied the study product to the right and left axilla each evening as directed and confirm reason for any missed doses.
  - Verbally confirm application process.
- Review concomitant medications/treatments.
- At Visit 11, remind subject to bring their study medication to next visit.
- Schedule the subject to return for the next study visit.

## 7.2.10 Visit 12: GSP6 (Day 43; End of Treatment) $\pm$ 2 Days

The following activities will be conducted:

- Collect vital signs (blood pressure, heart rate, respiratory rate and temperature) after subject has been seated for ≥2 minutes.
- Subject to complete the GSP assessment; will be conducted from 7:00 am to 11:00 am.
- Subject to complete HDSM-Ax assessment.
  - o Subject to complete PGI-S administered as Question #6 at the end of the HDSM-Ax questionnaire.
  - Subject to complete PGI-C administered as Question #7 at the end of the HDSM-Ax questionnaire.
- Subject to complete the DLQI questionnaire.
- Perform local tolerability assessments.
- Review changes to the subject's health (AEs).
- Collect subject's previously dispensed study product container, weigh with the applicator cap on, and record weight of container.
- Evaluate subject compliance:
  - Ask subjects whether they applied the study product to the right and left axilla each evening as directed and confirm reason for any missed doses.
  - o Verbally confirm application process.
- Collect samples for laboratory assessments (hematology, chemistry, and urinalysis).
- Perform UPT if applicable (FOCBP only). If positive, the subject shall be withdrawn from the study.
- Review concomitant medications/treatments.
- Schedule the subject to return for the next study visit.

## 7.2.11 Visit 13: Follow-up (Day 57) $\pm$ 3 Days

The following activities will be conducted:

- Collect vital signs (blood pressure, heart rate, respiratory rate and temperature) after subject has been seated for ≥2 minutes.
- Subject to complete the GSP assessment; will be conducted from 7:00 am to 11:00 am.
- Subject to complete HDSM-Ax assessment.
  - o Subject to complete PGI-S administered as Question #6 at the end of the HDSM-Ax questionnaire.
- Subjects  $\geq$  17 years of age to complete optional End of Study Survey.
- Perform local tolerability assessments.
- Review changes to the subject's health (AEs).
- Review concomitant medications/treatments.
- Discharge subject from the study.

#### 7.3 Unscheduled Visits

If a subject is seen for an unscheduled visit, an assessment and record of AEs should be completed, as appropriate. Additional evaluations should be performed as necessary, and the appropriate CRF pages should be completed.

## 7.4 Early Discontinuation of Subjects

It is the right and duty of the Investigator to discontinue a subject's participation if the subject's health or wellbeing is threatened by continuation in the study. In the event of premature discontinuation, the Investigator should determine the primary reason for discontinuation. A subject may be discontinued from the study if any of the following circumstances occur:

- The subject experiences a SAE rendering him or her unable to continue study participation.
- The subject experiences an AE that in the opinion of the Investigator may pose a significant risk for continued participation of the subject in the study.
- The subject is unable to physically or mentally tolerate the use of the investigational product.
- An exclusion criterion becomes apparent at any time during the study; the Medical Monitor must be contacted to discuss prior to discontinuing subject participation.
- The subject is not compliant with the study procedures; the Medical Monitor must be contacted to discuss prior to discontinuing subject participation.
- The subject voluntarily withdraws from the study. When possible, attempt to identify the reason the subject withdrew consent and document with particular attention paid to whether an underlying AE is at cause.
- The subject becomes pregnant.
- If for any reason per the Investigator's or the Sponsor's judgment, discontinuation is in the subject's best interest.

Subjects who discontinue the study prior to the completion of all treatment visits will be asked to complete the evaluations corresponding to Visit 12 (Day 43, End of Treatment). The Sponsor will be notified of early discontinuation as soon as possible during the study.

#### 8 RESPONSE MEASURES AND SUMMARY OF DATA COLLECTION METHODS

## 8.1 Safety Measures

The following safety assessment measures will be conducted as indicated in Section 7.1, Time and Events Table.

- Physical examination
- Vital signs (blood pressure, pulse rate, respiratory rate, and temperature)
- Laboratory tests (hematology, chemistry, urinalysis) and pregnancy testing in FOCBP
- Collection of AEs
- Local tolerability assessments

## 8.1.1 Physical Examination

Physical examination will include assessments of the head, eyes, ears, nose, throat, skin, thyroid, neurological, lungs, cardiovascular, abdomen (liver and spleen), lymph nodes, and extremities. Height and weight will also be measured and recorded.

#### 8.1.2 Vital Signs

Subjects should be seated for ≥2 minutes prior to measurements. Pulse rate (bpm) will be counted over 60 seconds. Blood pressure (mmHg) will be measured with a sphygmomanometer.

Vital sign measurements will include systolic and diastolic blood pressure, pulse rate, respiratory rate, and temperature.

## 8.1.3 Clinical Laboratory Assessments

Hematology, clinical chemistry, urinalysis, and additional parameters to be tested are listed below:

Hematology

| Trematorosy                  |  |                             |
|------------------------------|--|-----------------------------|
| Platelet count               | RBC Indices:                                     | Automated WBC Differential: |
| Red blood cell (RBC) count   | Mean corpuscular volume (MCV)                    | Neutrophils                 |
| White blood cell (WBC) count | Mean corpuscular hemoglobin (MCH)                | Lymphocytes                 |
| Reticulocyte count           | Mean corpuscular hemoglobin concentration (MCHC) | Monocytes                   |
| Hemoglobin                   |  | Eosinophils                 |
| Hematocrit                   |  | Basophils                   |

**Clinical Chemistry** 

| Blood urea nitrogen | Chloride                         | Alkaline phosphatase       |
|---------------------|----------------------------------|----------------------------|
| Creatinine          | Aspartate aminotransferase (AST) | Total and direct bilirubin |
| Sodium              | Alanine aminotransferase (ALT)   |                            |
| Potassium           | Gamma glutamyl transferase (GGT) |                            |

#### **Routine Urinalysis**

Bilirubin, color, appearance, glucose, ketones, leukocyte esterase, nitrite, occult blood, pH, protein, specific gravity, and urobilinogen

Microscopic examination (if blood or protein is abnormal)

#### **Other Screening Tests**

Urine Pregnancy Test (females of childbearing potential\* only, using UPT tests provided by the Sponsor.)

\* Females of childbearing potential for this study includes any female capable of becoming pregnant who has not undergone successful surgical sterilization (hysterectomy, bilateral tubal ligation [≥6 months prior to baseline], or bilateral oophorectomy) or is not postmenopausal (defined as amenorrhea ≥12 consecutive months).

All results will be reported and must be reviewed by the Investigator or designee. Abnormal results shall be assessed for clinical significance. Repeat laboratory testing may be requested at the discretion of the Investigator. If an AE should require laboratory testing, the results of the test should be obtained by the investigative site and filed in the subject's documentation.

#### **8.1.4** Adverse Events

Adverse events (AEs; see Section 9.2) will be collected for all untoward medical occurrences in a subject entered into this clinical study (e.g., signed consent), whether or not a pharmaceutical product has been administered. Any event, including local tolerability assessments (see Section 8.1.5), that requires specific treatment, results in interruption of treatment, or results in discontinuation of the subject from the study will also be reported as an AE.

Care will be taken not to introduce bias when detecting AEs and/or SAEs. Open-ended and non-leading verbal questioning of the subject is the preferred method to inquire about AE occurrence.

Appropriate questions include:

- "How are you feeling?"
- "Have you had any (other) medical problems since your last visit/contact?"
- "Have you taken any new medicines, other than those provided in this study, since your last visit/contact?"

#### 8.1.5 Local Tolerability Assessments

Local tolerability assessments (see Appendix 5) will be evaluated through assessment of symptoms at the drug application site. These assessments are to be performed for both axillae individually. Subject assessments will be made prior to the Investigator assessments.

**Subject Local Tolerability Assessments:** Subjects will be queried about whether any symptoms occurred at the study drug application site within the previous 24 hours and further whether any such symptoms persisted longer than 1 hour following study drug application. Standardized scales will be used to describe specifically the severity of any burning, stinging, or itching.

**Investigator Local Tolerability Assessments:** Investigators will observe for the existence of any significant local symptoms at the study drug application site. Significant local symptoms are defined as those not ordinarily observed following application of a topical product. Standardized scales will be used to describe specifically the severity of any erythema or scaling.

Local tolerability signs and symptoms that result in a subject requiring a concomitant therapy, interruption of treatment, or discontinuation from the study, will be reported as AEs.

## 8.1.6 Subject Assessments

Subjects must complete ALL self-assessments while at the clinic (i.e., HDSM-Ax, DLQI, PGI-S, PGI-C) prior to assessments being made by the Investigator. Please see Appendix 2 and Appendix 3 (HDSM-Ax by age; also includes PGI-S and PGI-C) and Appendix 4 (DLQI) for a full description of these assessments. Subjects will also have the option to complete an End of Study Survey. The HDSM-Ax, DLQI, PGI-S, and PGI-C assessments, as well as the optional End of Study Survey, will be collected electronically using a tablet device. Site personnel will be trained and a separate electronic clinical outcomes assessment (eCOA) manual will be supplied.

## 8.2 Summary of Methods of Data Collection

This protocol will utilize validated 21 Code of Federal Regulations (CFR) Part 11 compliant electronic data capture (EDC) software and eCOA software to collect required study data. The Investigator must ensure that data are properly recorded on each subject's eCRFs, eCOAs, and related documents. When changes or corrections are made in the eCRF, the EDC systems will maintain an audit trail of the person making the changes, the date and time of the change, and the reason for the change. Only individuals listed on the Delegation of Responsibilities Log with responsibility for eCRF completion may make entries in the eCRFs.

The Investigator or physician Sub-Investigator must electronically sign and date each subject's eCRF for each timepoint completed. Individuals who will be providing electronic signatures must first submit documentation with a handwritten signature acknowledging that their electronic signature is a legally binding equivalent to their handwritten signature.

## 8.3 Efficacy Measures

The following assessment measures will be conducted to evaluate the long-term efficacy of sofpironium bromide gel, 15% as indicated in the Procedures Section 7.1:

- HDSM-Ax as measured by the subject
- GSP as measured by the Investigator
- DLQI as measured by the subject (for subjects  $\geq$ 17 years of age)
- Patient Global Impression Scales; Severity (PGI-S) and Change (PGI-C)

## 9 ADVERSE EVENTS (AE) AND SERIOUS ADVERSE EVENTS (SAE)

## 9.1 Safety Evaluations

The Investigator is responsible for the appropriate medical care and the safety of subjects who have entered this study. The Investigator must document any AE experienced by subjects who have entered this study and report all SAEs to the CRO (see Section 9.3.1). Contact information for the Sponsor's Medical Monitor is provided on the protocol cover page.

#### 9.2 Adverse Events

#### 9.2.1 Definitions of Adverse Events

According to 21 CFR Parts 312.32 and 320.32 (IND Safety Reporting, Applicability of Requirements Regarding an "Investigational New Drug Application"), Food and Drug Administration (FDA) Guidance for Industry (Investigational New Drug Safety Reporting Requirements for Human Drug and Biological Products and Safety Reporting Requirements for Bioavailability and Bioequivalence Studies in Humans) (Federal Register/Vol. 75, No. 188/September 29, 2010) and International Council on Harmonisation (ICH) E2A (Clinical Safety and Data Management: Definitions and Standards for Expedited Reporting):

An adverse event (AE) means any untoward medical occurrence associated with the use of a drug in humans, whether or not considered drug related.

A suspected adverse reaction (SAR) means any AE for which there is a reasonable possibility that the drug caused the AE.

The following information should be considered when determining whether or not to classify a test result, medical condition, or other incident as an AE:

Adverse events will be recorded from the time of informed consent.

Abnormal laboratory values should not generally be recorded as AEs unless an intervention is required, the laboratory abnormality results in an SAE, the lab abnormality results in study termination or interruption/discontinuation of study treatment, or the lab abnormality is associated with clinical signs or symptoms. When recording an AE resulting from a laboratory abnormality, the resulting medical condition rather than the abnormality itself should be recorded (e.g., record "anemia" rather than "low hemoglobin").

Complications that occur in association with a protocol-mandated intervention (e.g., invasive procedures such as biopsies) should be recorded as AEs.

Whenever possible, the Investigator should group signs or symptoms that constitute a single diagnosis under a single event term. For example, cough, rhinitis, and sneezing might be grouped together as "upper respiratory tract infection." If possible, abnormal laboratory results that meet the definition of an AE (see above) should be reported as a clinical diagnosis rather than the abnormal value itself (e.g., "anemia" rather than "decreased blood count").

## 9.2.1.1 Documentation and Monitoring Adverse Events

All AEs encountered during the clinical trial following subject consent through the last study drug visit will be recorded on the appropriate Adverse Events eCRF.

## Special considerations:

Elective procedures or routinely scheduled treatments are not considered AEs. However, an untoward medical event occurring in association with a prescheduled elective procedure should be recorded as an AE.

A baseline condition is not considered an AE unless the condition worsens following study drug administration.

Death itself is not considered an AE; it is, instead, the outcome of an AE.

SAEs that are considered related (i.e., determined to be possibly, probably, or definitely related) to sofpironium bromide by the Investigator or Sponsor should be followed until the event resolves or stabilizes (see Section 9.4).

## 9.2.1.2 Assessment of Adverse Events

For each AE, the start and resolution dates, intensity, seriousness (i.e., whether the event meets the definition of an SAE [Section 9.3.1]), relationship of the event to the study drug, action taken regarding study drug, and outcome of the event will be documented on the eCRF.

#### **Intensity**

The following definitions should be used to assess and grade AE intensity, including laboratory abnormalities judged to be clinically significant.

| Severity | Grade | Description   |  |  |
|----------|-------|---|--|--|
| Mild     | 1     | Awareness of sign or symptom, but easily tolerated          |  |  |
| Moderate | 2     | Discomfort enough to cause interference with usual activity |  |  |

| Severity | Grade | Description  |
|----------|-------|--|
| Severe   | 3     | Incapacitating with inability to work or do usual activity |

Note: a severe adverse event is not necessarily serious.

## Relationship

The relationship of an AE to study drug should be assessed using the guidelines presented in the table below. An AE for which there has been no causal relationship reported will require follow-up to determine causality.

## **Adverse Event Relationships to Study Drug**

| Degree of Certainty | Description  |
|---------------------|--|
| Definitely Related  | An event that follows a reasonable temporal sequence from administration of the test article; that follows a known or expected response pattern to the test article; and that is confirmed by improvement on stopping or reducing the dosage, and reappearance of the event on repeated exposure (re-challenge).   |
| Probably Related    | An event that follows a reasonable temporal sequence from administration of the test article; that follows a known or expected response pattern to the test article; and that is confirmed by improvement on stopping or reducing the dosage of the test article; and that is unlikely to have been caused by concurrent/underlying illness or other drugs, procedures, or other causes. |
| Possibly Related    | An event that follows a reasonable temporal sequence from administration of the test article; that follows a known or expected response pattern to the test article; but may have been caused by concurrent/underlying illness, other drug, procedure, or other causes.  |
| Unlikely Related    | An event that does not follow a reasonable temporal sequence from administration of the test article; that does not follow a known or expected response pattern to the test article, or most likely was caused by concurrent/underlying illness, other drug, procedure, or other causes, because of their known effects.   |
| Not related         | An event almost certainly caused by concurrent/underlying illness, other drug, procedure, or other causes.   |

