### **Clinical Safety Conclusions**

In studies conducted to date, three concentrations of sofpironium bromide gel, 5%, 10%, and 15%, demonstrated comparably acceptable safety and tolerability. Treatment-emergent adverse events (TEAEs) were mostly mild or moderate in severity with fewer subjects reporting TEAEs in the 5% gel group relative to the 10% and 15% gel groups. No deaths or drug-related serious adverse reactions have been reported in any sofpironium bromide gel clinical studies. Six serious adverse events have been reported and all were determined to be unrelated to

sofpironium bromide gel administration.

Consistent with the soft drug design, a low incidence of systemic anticholinergic adverse events (AEs) has been found in all clinical studies of sofpironium bromide gel. The most common anticholinergic AE was dry mouth, and all anticholinergic AEs were expected. Of note, the anticholinergic AEs were predominantly mild or moderate in severity and transient in duration (i.e., resolving gradually with continued use). All TEAEs completely resolved spontaneously with treatment discontinuation. Local application site tolerability reactions of burning, itching, pain, erythema, and dryness at the axillae were predominantly minimal in severity and typically transient.

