Additional updates from the Investigator may be necessary as more information becomes available on the SAE, and all treatment-related SAEs will be followed until the acute event has resolved or stabilized, even if the subject discontinues study participation prior to the SAE resolution. Any new information or follow-up information pertaining to previously reported SAEs will be reported to the CRO Medical Monitor within 24 hours of becoming aware of the new or follow-up information. The new or follow-up information should be faxed to [contact] (US toll-free: [name]) or e-mailed to [contact].

Any SAE that occurs after study completion, and is considered by the Investigator to be related to sofpironium bromide, should be reported to the Sponsor.

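### All three related categories in the AE causality table require a known or expected response pattern, so an unexpected reaction cannot be coded related; one kind of expected reaction also fits no row

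*Protocol*

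**What the plan says.** Protocol Section 9.2.1.2 asks the investigator to grade each AE against a five-row table, which the text introduces as guidelines. Definitely, Probably and Possibly Related all require reasonable timing and a known or expected response pattern. They differ in what comes next:

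- Definitely Related adds "and that is confirmed by improvement on stopping or reducing the dosage, and reappearance of the event on repeated exposure (re-challenge".
- Probably Related adds "and that is confirmed by improvement on stopping or reducing the dosage of the test article", and requires that other causes be unlikely.
- Possibly Related has no dechallenge condition, but is for an event "that follows a known or expected response pattern to the test article; but may have been caused by concurrent/underlying illness", or by another drug, a procedure or something else.

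Unlikely Related lists three clauses: no reasonable timing, no known or expected pattern, or most likely another cause. Not Related is for events almost certainly due to something else.

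Three other places bear on the table. Section 9.2.1 states: "A suspected adverse reaction (SAR) means any AE for which there is a reasonable possibility that the drug caused the AE". Section 1 (Clinical Safety Conclusions) reports that the drug's anticholinergic AEs were predominantly mild or moderate and "transient in duration (i.e., resolving gradually with continued use". The special considerations in Section 9.2.1.1 show which rows count as related, in the context of follow-up: "SAEs that are considered related (i.e., determined to be possibly, probably, or definitely related".

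**The concern.** The table mixes two questions: whether the drug may have caused the event, and whether this kind of event is already recognised for the drug. A suspected adverse reaction under Section 9.2.1 needs only the first. If a recognised pattern is a precondition for every related row, a reaction not seen before is the one the table cannot call related, and finding such reactions is a main purpose of safety coding in a Phase 3 trial that enrols from age 9.

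The code is used in several places:

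- Protocol Section 10.4 and SAP Section 9.2 plan tables of treatment-related TEAEs and treatment-related serious TEAEs.
- SAP Section 9.2 also plots treatment-related TEAEs over time, by number of events and by number of subjects.
- Under Protocol Section 9.3.1, an SAE after study completion goes to the Sponsor if it meets this description: "Any SAE that occurs after study completion, and is considered by the Investigator to be related to sofpironium bromide". No Sponsor judgement is mentioned there as a back-up.

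The SAP gives no other rule for relatedness.

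**Working it through.** There is no stated figure to reproduce. The check codes each row as a set of conditions and asks which row each combination meets.

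| Row | Timing | Known or expected pattern | Improvement on stopping or reducing | Rechallenge | Other cause |
|---|---|---|---|---|---|
| Definitely | required | required | required | required | not stated |
| Probably | required | required | required | not needed | unlikely |
| Possibly | required | required | not needed | not needed | may have contributed |
| Unlikely | absent, and/or pattern absent; or other cause most likely | see left | not stated | not stated | see left |
| Not Related | not stated | not stated | not stated | not stated | almost certain |

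The semicolon between the first two clauses of Unlikely can be read as *and* or as *or*, so both readings were run. Timing is held as reasonable. There are three dechallenge histories (no improvement on stopping or reducing; improvement; improvement plus rechallenge) and two states of other cause (unlikely; possible), which gives 3 × 2 = 6 combinations for each pattern status.

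**Unexpected event (no known pattern).** A related row is available in 0 of 6 combinations, including improvement on stopping, reappearance on rechallenge and no other cause. Under the *or* reading all 6 are Unlikely; under the *and* reading all 6 have no row. The Section 9.2.1 definition carries no pattern condition, and that last combination is plainly a reasonable possibility. The two sections therefore give opposite answers for the same event.

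**Expected event (known pattern).** A related row is available in 5 of 6 combinations under both readings. The exception is an event with no improvement on stopping or reducing, because dosing continued, and with other causes unlikely:

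- Definitely and Probably fail on the dechallenge condition.
- Possibly fails because it is worded for events that may have another cause.
- Unlikely fails because timing and pattern are both present and no other cause is most likely.
- Not Related fails because no other cause is almost certain.

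If another cause may have contributed, the same event is Possibly Related. The order is reversed: the version with the stronger causal evidence has no code, and the version with the weaker evidence has one.

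Section 1 shows that resolution under continued use is a known course for the drug's anticholinergic AEs, and the action-taken list in Section 9.2.1.2 includes an entry for no action. So continued dosing through an event is foreseen. Leaving the field blank is not a way out, because Section 9.2.1.2 requires follow-up of any AE without a reported causality.

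The 0 of 6 and 5 of 6 count combinations of attributes, not subjects or events, and say nothing about frequency.

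**The case against.** The strongest reply is that the table is guidance under a column headed as a degree of certainty, and that an experienced investigator will choose Possibly Related for a plausible event whatever the pattern clause says. That may happen, and it limits the practical effect. It does not remove the contradiction with Section 9.2.1, since an investigator who follows the table as written reaches a different code.

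A reader might infer more than the documents support in four ways:

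- *That no related row fits any event that settles while dosing continues.* Possibly Related has no dechallenge condition and fits whenever another cause may have contributed.
- *That expected events are pushed into Unlikely.* With reasonable timing and a known pattern, Unlikely applies only if another cause is most likely. For unexpected events, Unlikely follows only under one of the two readings of its clauses.
- *That the uncodable expected event is the usual course.* Section 1 speaks of resolution with continued use, but says nothing about how often other causes could be excluded.
- *That a first-of-its-kind SAE could go unreported during the study.* Sections 9.3 and 9.3.1 require reporting within 24 hours, and Section 9.3.1 makes this independent of causality. Section 9.3.1 leaves expedited reporting to the Sponsor, and Sections 9.2.1.1 and 9.4 let Sponsor judgement as well as the investigator's trigger SAE follow-up.

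It also stands that most safety tables do not use the code. All TEAEs, serious TEAEs, severe TEAEs, events of special interest, anticholinergic TEAEs and local site reactions are tabulated by arm regardless of attribution, so a difference from vehicle stays visible.

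**Conclusion.** The point holds in two parts. Taken literally, an unexpected reaction cannot be coded related, which conflicts with the protocol's own definition of a suspected adverse reaction. Separately, an expected reaction that resolves on continued dosing with no plausible other cause meets none of the five rows. The outputs affected are the treatment-related and treatment-related serious TEAE tables, the treatment-related TEAE plots, and the reporting of SAEs after study completion. The efficacy analyses and the other safety tables are untouched.

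The documents do not allow the amount of miscoding to be estimated. The conclusion assumes that the rows are applied as worded, that no eCRF completion guide already overrides them, and that the TEAE tables count as related the same three rows that Section 9.2.1.1 names for SAEs, since the SAP does not say so. This should be corrected because the remedy is small, but it does not threaten the trial's main conclusions.

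**What to change.** Reconcile the table in Protocol Section 9.2.1.2 with the definition in Section 9.2.1:

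- In the three related rows, make a known or expected pattern supportive evidence, not a condition.
- In Probably Related, apply the dechallenge condition only when drug was in fact stopped or reduced.
- Let Possibly Related apply with or without another possible cause.
- In Unlikely Related, state how the first two clauses are joined, and bring the pattern clause into line with the related rows.
- Keep related as possibly, probably or definitely, and say so in SAP Section 9.2, so that the tables keep their structure.

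The cost is one reworded table, matching eCRF completion guidance and one sentence in the SAP. The related count will probably be somewhat higher, but the codes are assigned under blinding in both arms. Populations, endpoints, dosing and clinical management do not change.
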